#### **8.8 Electrocardiogram**

Twelve-lead ECG will be obtained as indicated per the SOE

Electrocardiograms should be done in triplicate after the subject has been resting comfortably in a supine position for a minimum of 8 minutes. The mean of triplicate results will be captured in the eCRF.

A repeat of ECGs (in triplicate) is permitted to confirm potentially spurious results, at the discretion of the Investigator. Repeat analysis results should be discussed with the Medical Monitor. Details on the conduct of ECGs is provided in the Study Reference Manual.

## 8.9 Physical Examination

Complete and symptom-directed physical examinations (urogenital exams not required) will be performed as indicated per the SOE

## 8.10 Ophthalmic Exams

Ophthalmic examinations will be performed per the SOE The ophthalmic exam is comprised of: anterior segment examination, including grading of anterior chamber inflammation according to the Standardization of Uveitis Nomenclature (SUN) Working Group Grading Scheme for Anterior Chamber Flare; OCI; FST; IOP; clinical lens grading using the Age-Related Eye Diseases Study (AREDS) Clinical Lens Grading System (ARLNS); posterior segment/fundus examination including grading inflammation in the vitreous using the NIH Grading Scale for Vitreous Haze.

Best Corrected Visual Acuity will also be assessed at specified time points as indicated per the SOE. The BCVA will be assessed using the BVRT and the ETDRS acuity test. The procedures for ophthalmic exams are outlined in the Study Reference Manual.

## 8.11 Optical Coherence Tomography

Changes in OCT findings are of relevance to the safety profile of QR-110. Optical Coherence Tomography images will be evaluated for changes in the remaining volume of ONL and foveal thickness as safety parameters. All OCT scans should be performed in accordance with the procedures outlined in the Image Acquisition and Submission Protocol.

The Medical Monitor should review all OCT scans, with particular attention to identifying changes including, remaining volume of ONL, foveal thickness, appearance of cystoid macular edema, or macular edema as compared to baseline.

## 8.12 Efficacy Assessments

Efficacy assessments include BCVA, mobility course, FST, OCI, PROs, PLR, and NIRAF.

If possible, photoreceptor outer segment layer thickness will be calculated from OCT images as a secondary efficacy parameter. This assessment will be conducted for those subjects for whom high quality imaging to evaluate this parameter can be obtained, as determined by the Investigator.

Subjects' assessment of the impact of their visual disability on general health-related outcomes as well as specific vision-related outcomes of daily living will be assessed for adult subjects by the VFQ-25 and for pediatric subjects by the CVAQC.

Secondary efficacy response criteria will be obtained as indicated per the SOE

## **9.0 ASSESSMENT OF SAFETY OR ADVERSE EVENTS AND SERIOUS ADVERSE EVENTS**

All subjects who receive study drug will be assessed for safety.

Investigators are responsible for monitoring the safety of subjects who have entered this study and for alerting the Sponsor regarding any event that seems unusual, even if this event may be considered an unanticipated benefit to the subject. The Investigator is responsible for appropriate medical care of subjects during the study.

### **9.1 Review of Safety Data**

A program-specific review of safety data, which may include independent experts, will be in place to assess emerging data from clinical studies on an ongoing basis.

### **9.2 Definitions of Adverse Event, Serious Adverse Event, and Suspected Unexpected Serious Adverse Event**

#### **9.2.1 Adverse Events**

An AE is any untoward medical occurrence associated with the use of a drug in humans, whether considered drug related or not. Adverse events can include any unfavorable, noxious, unintended sign, symptom, or disease temporally associated with use of a study drug or other protocol-imposed intervention, regardless of attribution. Adverse events may be spontaneously reported by the subject, discovered by Investigator questioning, or detected through physical examination, laboratory test, or other means.

Adverse events include:

- Pre-existing medical conditions judged by the Investigator to have worsened in severity or frequency or changed in character during the protocol-specified AE reporting period (as specified in [Section 9.4.1](#))
- Adverse events not previously observed in the subject that emerge during the protocol-specified AE reporting period (as specified in [Section 9.4.1](#))
- Complications that occur as a result of protocol-mandated interventions (eg, invasive procedures such as IVT injections)
- Adverse events that occur prior to study treatment that are related to a protocol-mandated intervention (eg, invasive procedures such as blood draws, anesthesia prior to IVT injection)

### 9.2.2 Serious Adverse Events

A serious adverse event (SAE) is any AE that suggests a significant hazard, contraindication, side effect, or precaution regardless of the relationship to study drug. An SAE is any AE that results in any of the following outcomes:

- Death
- Life-threatening AE. This definition implies that the subject, in the view of the Investigator, is at immediate risk of death from the event as it occurred. It does not include an event that, had it occurred in a more severe form, might have caused death
- Inpatient hospitalization or prolongs existing hospitalization, except for hospitalization for planned post dose sample collections
- Persistent or significant disability/incapacity (ie, the AE results in substantial disruption of the subject's ability to conduct normal life functions)
- Congenital anomaly or birth defect. This serious criterion applies if a congenital anomaly/birth defect is diagnosed in a child born to a female subject, or a female partner of a male subject exposed to the study drug
- Other important medical events. Medical and scientific judgment should determine whether an AE should be classified as serious in other situations, such as important medical events that may not be immediately life threatening or result in death or hospitalization but may jeopardize the subject or require intervention to prevent one of the outcomes listed in the definition above.

All AEs that do not meet any of the criteria for serious should be regarded as non-serious AEs.

The terms “severe” and “serious” are not synonymous. Severity refers to the intensity of an AE (as in mild, moderate, or severe pain); the event itself may be of relatively minor medical significance (such as severe headache) ([Section 9.3.1](#)). “Serious” is a regulatory definition and is based on subject or event outcome or action criteria usually associated with events that pose a threat to a subject’s life or vital functions. Seriousness (not severity) serves as the guide for defining regulatory reporting obligations.

Severity and seriousness should be independently assessed when recording AEs and SAEs on the AE eCRF and SAE form.

### 9.2.3 Suspected Unexpected Serious Adverse Reaction Definition

A suspected unexpected serious adverse reaction (SUSAR) is a suspected unexpected serious adverse reaction. In order to be qualified as a SUSAR, the AE must meet 3 criteria: the event is serious, there is a certain degree of probability that the event is a reaction to the study drug being researched, and the nature and severity of the reaction are not in agreement with the product

information (ie, the reaction is unexpected as per the reference safety information). All SUSARs will be reported as required to the Competent Authorities and to the Ethics Committee (EC)/Institutional Review Boards (IRBs) of the countries and centers concerned.

#### **9.2.4 Adverse Events of Special Interest**

The following are considered AEs of special interest, based on the route of administration and safety profile for QR-110.

## 9.3 Assessment of Adverse Events

The Investigator is responsible for assessing the severity and causality of AEs.

### 9.3.1 Assessment of Severity (Intensity) of Adverse Events

On the AE eCRF, the Investigator will use the adjectives MILD, MODERATE, or SEVERE to describe the maximum intensity of the AE. For purposes of consistency, these intensity grades are defined as follows:

- MILD: Does not interfere with subject's usual function.
- MODERATE: Interferes to some extent with subject's usual function.
- SEVERE: Interferes significantly with subject's usual function.

As described previously in [Section 9.2.2](#), note the distinction between the severity and the seriousness of AE. A severe event is not necessarily a serious event. For example, a headache may be severe (interferes significantly with subject's usual function) but would not be classified as serious unless it met one of the criteria for SAEs, listed above in [Section 9.2.2](#).

### 9.3.2 Assessment of the Relationship of Adverse Events to Study Drug

The Investigator will make a causality assessment about the relationship of each AE to study drug. To ensure consistency of AE and SAE causality assessments, Investigators should apply the following general guideline:

**Not Related:** The AE has an etiology other than the study drug (eg, preexisting medical condition, underlying disease, intercurrent illness, or concomitant medication); and/or the AE has no plausible temporal relationship to administration of the study drug (eg, cancer diagnosed 2 days after first dose of study drug).

**Possibly Related:** An AE that follows a reasonable temporal sequence from administration of the study drug, follows a known or expected response pattern to the study drug, but that could readily have been produced by a number of other factors.

**Probably Related:** An AE that is clearly related to the study drug or its administration (ie, an event that follows a reasonable temporal sequence from administration of the study intervention, follows a known or expected response pattern to the suspected intervention, that is confirmed by improvement on stopping and reappearance of the event on repeated exposure and that could not be reasonably explained by the known characteristics of the subject's clinical state).

**Definitely Related:** The AE is clearly related to the study drug; a re-challenge confirms the association (not required or desirable in some circumstances but provides strong evidence when it happens).

For all AEs and SAEs, Investigators will make separate assessments of causality about the relationship of the event to study drug and to drug administration (ie, IVT injection).

**Note:** The Investigator's assessment of causality for individual AE reports is part of the study documentation process and will be recorded in the subject's medical record, AE eCRF, and SAE form if applicable. Adverse events recorded without the Investigator's assessment of the relationship to study drug will be followed up until causality is assigned.

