#### 4.7.1. Adverse Events

Adverse events will be coded using the Medical Dictionary for Regulatory Activities (MedDRA) Version 20.0 and displayed in tables and listings using System/Organ/Class (SOC) and Preferred Term.

Adverse events are summarized by subject frequencies, therefore, in any tabulation, a subject contributes only once to the count for a given adverse event (SOC or preferred term).

A treatment emergent adverse event (TEAE) is defined as an event that was not present prior to administration of the first dose of study drug and present after the first dose or if it represents the exacerbation of an event that was present prior to the first dose.

The number and percentage of subjects with any TEAE, with any TEAEs assessed by the Investigator as related to study drug and those related to drug administration (definite, probable, or possible relationship), and with any serious adverse event will be summarized by treatment group and overall. Deaths, TEAE severity, seriousness, outcomes (resolved, resolved with sequelae, not resolved, resolving, fatal and unknown) and study discontinuation due to TEAE will also be tabulated by treatment group. In these tabulations, each subject will contribute only once (i.e., the most related occurrence or the most severe occurrence) to each of the counts in the descriptive analysis, regardless of the number of episodes. No formal hypothesis-testing analysis of adverse events will be performed.

Missing or partial start and end dates will be imputed as described in Section 4.2.9.3 before determining whether an AE is treatment emergent. For subjects with an actual or imputed AE start date on Day 1, the

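### Protocol 9.3.2 requires a recognised reaction pattern for two of its three related grades, so a suspected new type of reaction fits only the top grade or no related grade

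*Protocol*

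**What the plan says.** Protocol 9.3.2 gives investigators a four-grade causality scale, offered as guidance so that assessments are consistent.

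- **Not Related**: "The AE has an etiology other than the study drug", and/or the timing is implausible. Underlying disease is one of the listed examples of another cause.
- **Possibly Related**: the event "follows a known or expected response pattern to the study drug, but that could readily have been produced by a number of other factors", and its timing is reasonable.
- **Probably Related**: clearly linked to the drug or to its administration. The event has reasonable timing and "follows a known or expected response pattern to the suspected intervention", the link is one "that is confirmed by improvement on stopping and reappearance of the event on repeated exposure", and the subject's clinical state does not reasonably explain it.
- **Definitely Related**: clearly linked to the drug; "a re-challenge confirms the association (not required or desirable in some circumstances but provides strong evidence when it happens". No pattern is mentioned.

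The same section asks for separate causality judgements for the drug and for the IVT injection, and says that a missing judgement is pursued until one is given.

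Protocol 9.2.3 defines a SUSAR by three conditions: the event is serious, it is unexpected against the reference safety information, and "there is a certain degree of probability that the event is a reaction to the study drug being researched".

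SAP 4.7.1 tabulates TEAEs "related to study drug and those related to drug administration (definite, probable, or possible relationship"). Protocol 10.6.1 and SAP 4.7.1 count an event as related if it is graded at least possible or if the grade is missing.

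**The concern.** A causality scale should let an investigator record a moderate suspicion about an event not seen before. Here the two grades that express moderate suspicion are reserved for events that already look like known reactions. The second-highest grade also asks for more evidence than the highest.

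Three outputs use these grades directly:

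- the related and not-related TEAE tables (Protocol 10.6.1, SAP 4.7.1);
- follow-up of related events that persist beyond 3 months after the last dose (Protocol 9.4.1);
- reporting of SAEs that arise after participation, which turns on the word possibly (Protocol 9.5).

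The grades also inform SUSAR classification and the benefit/risk assessment in Protocol 4.2.2. The primary objective is long-term safety, so new reactions are what the scale most needs to be able to hold.

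**Working it through.** The plan states no figure to reproduce. The check is to apply the four definitions literally to every type of event with plausible timing.

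**Inputs (all Protocol 9.3.2).** Three yes/no features: recognised pattern; positive de-challenge and re-challenge; another plausible cause. That gives 2 × 2 × 2 = 8 profiles.

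**Reading used.** Possibly needs a recognised pattern and another ready explanation. Probably needs a recognised pattern, both challenge results and no reasonable alternative. Definitely needs a clear link, shown by re-challenge or by judgement, and is taken to be closed when another cause is plausible.

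| Recognised pattern | De-/re-challenge positive | Other cause plausible | Related grades open |
|---|---|---|---|
| Yes | Yes | Yes | Possibly |
| Yes | Yes | No | Probably, Definitely |
| Yes | No | Yes | Possibly |
| Yes | No | No | Definitely, by judgement only |
| No | Yes | Yes | None |
| No | Yes | No | Definitely |
| No | No | Yes | None |
| No | No | No | Definitely, by judgement only |

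**Results.**

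1. Unrecognised pattern: 0 of 4 profiles can be Possibly or Probably. Two can only be Definitely, and two have no related grade.
2. No positive de-/re-challenge, which includes irreversible events: 0 of 4 can be Probably. The one with a recognised pattern and another cause is still Possibly, so it counts as related.
3. If a positive re-challenge is taken to settle the matter despite another plausible cause, the fifth row becomes Definitely and only the seventh row stays empty.

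These are counts of profiles, not frequencies of events.

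**Is a competing cause likely?** Protocol 9.3.2 names underlying disease as another cause, and Protocol 2.0 describes slow progressive loss of remaining vision. For a new visual or retinal event, the profile with no related grade is easy to meet.

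**Does the missing-grade rule help?** Seldom. A blank counts as related in the tables, but 9.3.2 has blanks queried until a grade is given.

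**Comparison with 9.2.3.** A SUSAR needs some probability of a drug cause and must be unexpected. The two grades that express intermediate probability both require a recognised pattern.

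**Size per subject.** With the maximum of 11 subjects (Protocol 5.1), one reclassified subject moves an overall related-TEAE rate by 1/11 = 9.1 percentage points; two move it by 2/11 = 18.2 and three by 3/11 = 27.3. Tables by treatment group have smaller denominators and therefore larger steps. The exact (Clopper-Pearson) 95% interval is 0.2% to 41.3% for 1/11 and 0% to 28.5% for 0/11. These intervals reflect the sample size, not the wording defect.

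**The case against.** A reader might infer four stronger things, and the documents do not support them.

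- **Irreversible events have no related grade.** They do. Irreversibility closes only Probably. A known type of event with another possible cause is still Possibly and is counted as related.
- **New reactions are pushed to Not Related.** That grade requires that the event has another cause or implausible timing. A merely conceivable alternative does not meet it. The scale leaves a gap rather than an instruction to grade such events as unrelated, and Definitely stays open when there is no other cause.
- **9.3.2 contradicts 9.2.3.** Section 9.2.3 does not cite the scale, and its unexpectedness is judged against the reference safety information. A known reaction of unlisted severity can be unexpected there and still be Possibly, and a serious unexpected event graded Definitely can be a SUSAR. The tension concerns new types of event.
- **Related events are undercounted.** The scale is guidance, and the number of events affected cannot be derived.

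The protocol also has safeguards that do not rest on the grade. The primary endpoints cover all ocular and non-ocular AEs (4.1.1). Every SAE is notified whatever its suspected cause, with a rationale for the causality judgement (9.5). Investigators must alert the sponsor to unusual events (9.0). The safety profile draws on all AEs except those plainly unrelated (10.1). Treatment may be stopped for any AE (4.2.2).

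All of this stands, and it limits the consequences. It does not supply a grade for a suspected new reaction with a competing explanation, and it does not explain why Probably demands more than Definitely. Guidance meant to make ratings consistent should not leave a case that sites must resolve by improvisation.

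**Conclusion.** The defect is real and narrow: two of the three related grades exclude any event without a recognised pattern, and the grades are out of order on re-challenge. This is inconsistent with what 9.2.3 needs.

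The consequence is a risk, not a shown loss, of undercounting related TEAEs, related events followed beyond 3 months and post-study SAE reports. Each affected subject is worth 9.1 points at the maximum sample size; the number affected is unknown. The primary endpoint and SAE notification are untouched.

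The conclusion assumes that sites apply the definitions as written; looser use would shrink the effect and make ratings less comparable between sites. It should be fixed, but it does not threaten the main safety results.

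**What to change.** Amend Protocol 9.3.2:

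- In Possibly and Probably, make a recognised pattern supportive evidence, not a condition.
- In Probably, make de-challenge and re-challenge supportive, not required.
- Order the grades so that each step up asks for at least as much certainty as the one below.
- Take the reference to administration out of the drug scale, and apply the same four definitions separately to the drug and to the IVT injection.
- Reconcile the wording with 9.2.3, so that a reaction can be recorded as both suspected and unexpected.

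SAP 4.7.1 uses only the grade labels and needs no change of method.

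If recorded events are re-assessed, re-confirm causality for every event with plausible timing after an injection, whatever its recorded grade. Querying only those graded Not Related could move the count in one direction only, and the study is open-label. Keep and report both the recorded and the re-confirmed ratings.

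The cost is a wording amendment, one round of queries in at most 11 subjects, and a possible small change in the related-event count.

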### **9.3.3 Assessment of the Outcome of Adverse Events**

The Investigator will record the outcome of AEs and SAEs using the following criteria:

- **Recovered/resolved:** The subject has fully recovered from the event, with no residual effects observable.
- **Recovered/resolved with sequelae:** The subject has recovered from the event, but with residual sequelae effects observable.
- **Not recovered/resolved:** Effects of the event are still present.
- **Recovering/resolving:** The subject has improved but has not fully recovered from the event.
- **Fatal:** The death is related to the event.
- **Unknown:** The outcome of the event is unknown to the reporter (eg, subject was lost to follow-up).

### **9.4 Reporting of Adverse Events**

The Investigator is responsible for ensuring that all AEs and SAEs are recorded in the subject's medical record, AE eCRF, and/or SAE form, and reported to the Sponsor in accordance with protocol instructions.

#### **9.4.1 Adverse Event Reporting Period**

Any event/condition noted once the subject receives their first dose of study drug in the contralateral eye will be captured as an AE.

In the first treated eye all events/conditions will be captured as an AE as treatment continues from study PQ-110-001.

All AEs and SAEs regardless of attribution will be collected until at least 3 months following the last administration of study drug or the subject's EOS visit, whichever is later. At the last scheduled visit, the Investigator should instruct each subject to report to the Investigator any subsequent AEs/SAEs that the subject's personal physician believes could be related to prior study treatment.

Adverse events and SAEs related to study drug that persist > 3 months after the last study drug dose should be followed until resolution or until they return to baseline, stabilize, the subject is lost to follow-up, or it has been determined that the study drug or participation is not the cause of the AE/SAE.

Resolution of AEs and SAEs (with dates) should be documented on the AE eCRF and SAE form (if applicable) and in the subject's medical record to facilitate source data verification.

For some SAEs, the Sponsor or its designee may follow-up by telephone, facsimile, electronic mail, and/or a monitoring visit to obtain additional case details deemed necessary to appropriately evaluate the SAE report (eg, hospital discharge summary, consultant report, or autopsy report).

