### 8.1 Adverse Events

Information regarding occurrence of AEs will be captured throughout the study. Duration (start and stop dates), severity/grade, outcome, treatment and relationship to study drug will be recorded. Refer to [Section 9.0](#), Assessment of Safety or Adverse Events and Serious Adverse Events.

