#### **9.4.2 Eliciting Adverse Events**

A consistent methodology of non-directive questioning for eliciting AEs at all subject evaluation time points should be adopted. Examples of non-directive questions include:

*“How have you felt since your last clinic visit?”*

*“Have you had any new or changed health problems since you were last here?”*

Age-appropriate non-directive questions should be employed for eliciting AEs from pediatric subjects. Non-directive questions may also be used to elicit AEs from parents/caregivers of pediatric subjects, at the discretion of the Investigator.

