### **9.5 Serious Adverse Events Notification**

For all SAEs, regardless of suspected causality, an SAE form must be completed (or faxed if using paper form) within 24 hours of discovery of the event to:

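### Read literally, Protocol 9.4.1 starts AE capture outside the first treated eye only at the first contralateral-eye dose, in conflict with Protocol 8.1 and 9.4.2 and the SAP 4.7.1 safety tables

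*Protocol*

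**What the plan says.** Protocol 9.4.1 contains two statements about when capture begins and one about when it ends.

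- Tied to the contralateral dose: "Any event/condition noted once the subject receives their first dose of study drug in the contralateral eye will be captured as an AE".
- For the other eye: "In the first treated eye all events/conditions will be captured as an AE as treatment continues from study PQ-110-001".
- The end: "All AEs and SAEs regardless of attribution will be collected until at least 3 months following the last administration of study drug", or until the EOS visit if that comes later. This sentence gives no start.

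Other protocol sections are general. Section 8.1 states: "Information regarding occurrence of AEs will be captured throughout the study". Section 9.4 states: "The Investigator is responsible for ensuring that all AEs and SAEs are recorded". Section 9.4.2 asks for a consistent method of "eliciting AEs at all subject evaluation time points". Section 9.5 states: "For all SAEs, regardless of suspected causality, an SAE form must be completed". Section 9.2.1 also lists, as AEs, "Adverse events that occur prior to study treatment that are related to a protocol-mandated intervention". Section 9.4.3.5 treats a condition as preexisting if the subject already has it when the study starts.

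On the analysis side, SAP 4.7.1 plans TEAE summaries for all non-ocular events and, separately, for ocular events in four eye strata: the first treated eye, the treated contralateral eye before its first dose in the study, the same eye after that dose, and the contralateral eye that is not treated. SAP 3.1 admits a subject to the Safety Population on PQ-110-001 exposure plus enrolment here, so a subject whose contralateral eye is never dosed stays in.

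**The concern.** The two start rules in 9.4.1 read as a contrast: everything in the first treated eye, but only what follows the contralateral dose elsewhere. The SAP nevertheless plans to report what happened before that dose and in eyes that never received it.

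At stake are the primary endpoints, which are how often ocular and non-ocular AEs occur and how severe they are. A site that follows 9.4.1 literally may leave events unrecorded that a site following 8.1 and 9.4.2 would record. In the tables, a zero arising because nothing was collected would look the same as a zero arising because nothing happened.

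Delayed or withheld contralateral dosing is foreseen. Protocol 4.2 leaves initiation in that eye to a case-by-case decision, Protocol 4.2.1.3 provides for assessing both eyes when the contralateral eye is untreated, and SAP 4.2.2 has a non-treated contralateral group.

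**Working it through.** There is no stated figure to reproduce, so the check is a comparison of text.

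**Step 1: what 9.4.1 covers.** In its first sentence, the phrase about the contralateral eye can attach to the dose or to the event.

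| Event | 9.4.1, phrase attached to the dose | 9.4.1, phrase attached to the event | Tabulated in SAP 4.7.1 |
|---|---|---|---|
| First treated eye | Covered, continuing from PQ-110-001 | Same | Yes |
| Contralateral eye after its first dose | Covered | Covered | Yes |
| Contralateral eye before its first dose | No start | From the subject's first dose (eye and study not named) | Yes, own stratum |
| Contralateral eye never dosed | No start | May be covered, from the subject's first dose | Yes, own stratum |
| Non-ocular, after a contralateral dose | Covered | No start | Yes |
| Non-ocular, contralateral eye not yet or never dosed | No start | No start | Yes |

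Neither reading gives a start for every row that the SAP tabulates. The second reading moves the gap to non-ocular events.

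**Step 2: whether other sections settle it.** Sections 8.1, 9.4 and 9.4.2 reach every row, and 9.5 does so for SAEs. However, the 9.2.1 bullets on new and worsened events refer back to the 9.4.1 period, and so does the recording of deaths in 9.4.3.4. The circularity is partial, because the opening definition in 9.2.1 is broader and its list is inclusive. The pre-treatment bullet in 9.2.1 is limited to events related to a protocol-mandated intervention. Under 9.4.3.5, an event arising after study start but before the contralateral dose is not preexisting, yet on the literal reading 9.4.1 does not capture it either.

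**Step 3: how many subjects.** Protocol 5.1 caps enrolment at 11. Protocol 7.2 schedules contralateral dosing on Day 1, which makes the gap close to nil for a subject dosed on plan. Let k be the number with delayed or withheld contralateral dosing. The documents do not give k, so it runs from 0 to 11. With all 11 enrolled, the share is k/11: 0/11 = 0%, 1/11 = 9.1%, 11/11 = 100%. These are shares of subjects, not of events missed. No event rate can be derived.

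**Step 4: the related SAP anchor.** SAP 4.7.1 defines general and non-ocular TEAEs by the first dose without naming eye or study, although every subject was dosed in PQ-110-001. It also calls events before the contralateral eye's first dose TEAEs, which contradicts the definition if the anchor is that eye's own dose. Protocol 7.2 places the first treated eye's dose 3 months after the contralateral dose, so a subject without a Day 1 contralateral dose may have no Day 1 dose at all. Yet SAP 4.2.9.3.1 imputes a completely missing AE start to Day 1 when the event did not end before dosing on that day, while its fallback for partial dates uses the date of first dose. For such a subject the two rules give different dates, and the Day 1 rule can place the start before any PQ-110-002 dose. SAP 4.2.9 says the imputation is meant to fall after dosing.

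**The case against.** The strongest reply is that the protocol does direct collection. Sections 8.1, 9.4, 9.4.2 and 9.5 are operative text with no condition on eye or dose. Section 9.4.1 says what will be captured and nowhere says that anything else is excluded. The schedule of events, to which the timing of assessments is delegated, is not visible and might state a start. On plan, the contralateral eye is dosed first, on Day 1. The SAP's own strata, and its imputation of some missing starts to the consent date, show that the sponsor expects such records.

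All of this stands, and it makes the point a conflict between sections. It does not dispose of the point, because the general sections partly depend on the one section that defines the reporting period, and two sites could read them differently in good faith.

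Three stronger readings are tempting and unsupported.

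- A reader might infer that no rule requires these events to be collected. Section 8.1 alone refutes that.
- A reader might infer that half the ocular safety output is compromised, since two of the four eye strata lack a start on the literal reading: 9 ocular tables x 4 strata = 36 sections, of which 9 x 2 = 18. That counts table shells. It is the same whether 0 or 11 subjects are affected, and the second reading of 9.4.1 may cover the never-dosed stratum.
- A reader might infer that events were missed. Nothing in the documents shows it.

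**Conclusion.** The inconsistency is real and should be fixed, with medium confidence. On either reading, 9.4.1 fails to give a start for some primary-endpoint events that 8.1 and 9.4.2 direct sites to collect and that SAP 4.7.1 reports. The practical size is unknown and may be nil. It is near zero if every contralateral eye is dosed on Day 1, and grows only with the number of subjects whose contralateral dosing is late or absent and whose site applied 9.4.1 literally. The conclusion assumes that the unseen schedule of events does not state a start that overrides 9.4.1.

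The SAP anchor issue is secondary. It concerns how recorded events are classified, and its Day 1 element matters only for a subject with no Day 1 dose and an AE with a completely missing start date.

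**What to change.** **Protocol 9.4.1.** Reword it to match 8.1: all ocular AEs in both eyes, and all non-ocular AEs and SAEs, are collected from entry into PQ-110-002 (Screening/Day 1), whether or not the contralateral eye is dosed. Add that events already recorded in PQ-110-001 are not entered again. This is needed because the Screening/Day 1 visit should also be the PQ-110-001 EOS visit. Check 9.2.1 and 9.4.3.5 against the new wording.

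**SAP 4.7.1 and 4.2.9.3.1.** Name the dose, by eye and study, that anchors treatment emergence. For a completely missing AE start in a subject with no Day 1 dose, use the date of that dose instead of Day 1. Where the anchor is eye-specific, label earlier events in that eye as AEs, not TEAEs. Footnote pre-dose or non-treated-eye cells only if site records show that events were not collected.

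**Cost.** A short amendment, which under Protocol 13.2 needs IRB/EC approval before it takes effect, SAP wording changes, and a few more eCRF entries. No additional eye assessments are needed, because both eyes are already examined. The amendment works only prospectively and cannot recover events that were never recorded.
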